related concerns. The research staff will contact the participant 1 day and 7 days after completion of the EMG test to document any adverse events the participant may have had following the testing. Responses will be documented in the EMR and serious adverse events will be reported to the study sponsor and IRB within 24 hours. Adverse events which occur more than 5 days after the EMG test will not be considered related to the study intervention, unless the investigator suspects a potential link.

Sleep Study

All healthy study participants selected for the study will be required to complete an overnight stay for an in-laboratory Polysomnogram ("PSG").

Study Endpoints

Primary Endpoint

Proof of diagnostic consistency using both the TM-EMG sensor and NEMG in neuromuscular disorders of the oropharyngeal muscles.

TM-EMG and NEMG data will be analyzed offline upon completion of testing by [name]. Analysis will include the presence of spontaneous activity (fibrillation potentials and positive sharp waves), MUP morphology (number phases, duration and amplitude) and recruitment pattern. MUP morphology will be analyzed manually. Each recording will be labeled as a normal or abnormal study. Abnormal studies will be classified into active or chronic neurogenic changes or myopathic changes.

Secondary Endpoint

Proof that participants with known OSA exhibit EMG findings different from healthy participants and that these findings can be detected using both the needle electrode and the transmembrane sensor.

Analysis results will be compared between the healthy cohort and the neurologic disorders cohort; and between the healthy cohort and the OSA cohort.

Sample Size Calculation

Given that this is a novel EMG testing technique, a formal sample size calculation was not performed. The sample size chosen for this study was based on what would be reasonably feasible given constraints in areas such as funding and recruiting. The results from this pilot study will enable design of a larger, multi-site study adequately powered to show the diagnostic usefulness of TM-EMG.

Statistical Methods

All data will be examined to determine if there are any missing or non-plausible values, and these will be removed. Summary statistics will be calculated, including means or medians, minimums and maximums, standard deviations, and interquartile ranges.

The distribution of EMG findings in OSA will be presented as descriptive statistics.

ADVERSE EVENT MONITORING

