(CFR). The Principal Investigator will assure that no deviation from, or changes to the protocol will take place without prior agreement from the sponsor and documented approval from the Institutional Review Board (IRB), except where necessary to eliminate an immediate hazard(s) to the trial participants. The protocol, informed consent form(s), recruitment materials, and all participant materials will be submitted to the IRB for review and approval. Approval of both the protocol and the consent form must be obtained before any participant is enrolled. Any amendment to the protocol will require review and approval by the IRB before the changes are implemented to the study. All changes to the consent form will be IRB approved; a determination will be made regarding whether a new consent needs to be obtained from participants who provided consent, using a previously approved consent form.

Confidentiality, Data Access, and Declaration of Interests

Participant confidentiality will be strictly maintained throughout the study. All study records will be de-identified to maximum capability, and all study charts will be kept under lock-and-key in a secure office. The study charts will not contain any protected health information (PHI), and each participant will be identified only according to initials and unique study identifier. Following completion of the trial, all data will be kept by SENTA Clinic for two (2) years, as mandated. Electronic data will be stored on password-protected computers using the SENTA Clinic's secure servers. Access to trial data will be available to study investigators, research assistants, and statisticians; however, this data will be de-identified to the maximum of the investigators' capabilities. Finally, each investigator will declare any financial or other conflicts of interests prior to study onset, and at completion.

Dissemination Policy

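### The protocol does not require the EMG reader to be masked to cohort or to the paired recording and sets no reading order, so reader expectation can plausibly inflate both TM-EMG/NEMG agreement and the cohort differences

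*Combined protocol and SAP*

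**What the plan says.** Under Study Endpoints, Primary Endpoint, the protocol says that "TM-EMG and NEMG data will be analyzed offline upon completion of testing" by one named person (the name is removed). It adds: "MUP morphology will be analyzed manually. Each recording will be labeled as a normal or abnormal study". Abnormal recordings are then sorted as neurogenic (active or chronic) or myopathic. No numeric cut-offs are given.

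These readings supply both endpoints. The primary endpoint is "Proof of diagnostic consistency using both the TM-EMG sensor and NEMG in neuromuscular disorders of the oropharyngeal muscles". Under Secondary Endpoint, "Analysis results will be compared between the healthy cohort and the neurologic disorders cohort; and between the healthy cohort and the OSA cohort".

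The nearest text to masking is under Confidentiality, Data Access, and Declaration of Interests. There, "All study records will be de-identified to maximum capability", and "each participant will be identified only according to initials and unique study identifier". The same section says that "Access to trial data will be available to study investigators, research assistants, and statisticians", with the qualification that these data are de-identified as far as the investigators are able.

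**The concern.** The label is a judgement made by hand without stated limits, and the protocol says in advance what it expects to find. The Study Hypothesis expects the two methods to give similar diagnostic findings and OSA to show neurogenic changes. The background section lists muscular dystrophy among the myopathies and ALS among the neurologic disorders, so knowing the diagnosis suggests the label.

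This opens two routes to bias. A reader who sees one tracing of a pair may lean towards the same label for the other. A reader who knows the cohort may lean towards the expected label on both tracings, which can raise agreement and also widen cohort differences.

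At stake are the consistency finding and the comparisons of the healthy cohort with the other two. The plan is descriptive, so what would be inflated is a descriptive proportion or difference rather than a type I error rate. The results still have a use beyond this trial: under Sample Size Calculation, "The results from this pilot study will enable design of a larger, multi-site study".

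**Working it through.** **1. What the text covers.** The whole protocol was read for masking, independent or repeated reading, and reading order.

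- *Reader:* one removed name; no statement of what the reader may know.
- *Masking to cohort or to the paired recording:* none stated.
- *Reading order or separate sessions:* none stated. EMG Testing Procedure fixes the order of acquisition (TM-EMG by the co-investigator, then TM-EMG followed by the needle at each muscle by the principal investigator). That is not an order of reading.
- *De-identification:* a confidentiality rule. If initials and study identifier stay on the files, a participant's TM-EMG and NEMG recordings can plausibly be linked. No step is stated that withholds cohort until reading is finished.

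Only a name is removed from the sentence on who reads. The text around it is intact, so removal does not explain the gap.

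**2. Planned recordings, if every test is completed.** Study Summary gives 10 neuromuscular, 5 OSA and 8 healthy participants: 10 + 5 + 8 = 23.

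- NEMG: 4 sites each (palatoglossus and genioglossus, both sides), so 4 × 23 = 92.
- TM-EMG: 4 by the co-investigator + 6 by the principal investigator = 10 each, so 10 × 23 = 230.
- Total: 230 + 92 = 322. At about 10 seconds each, 322 × 10 = 3,220 seconds, or about 54 minutes of trace.
- Paired sites: 4 × 10 = 40 in the neuromuscular cohort and 92 overall, clustered within participants. Each paired site has two TM-EMG recordings, and the protocol does not say which is compared with the needle.

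**3. Why the size cannot be derived.** Let *a* be the agreement under masked reading and *c* the share of discordant second readings pulled to match the first. Then observed agreement = *a* + (1 − *a*)*c*, and the rise is (1 − *a*)*c*. The documents give neither input. As an illustration on assumed values only:

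- *a* = 0.80, *c* = 0.25: 0.80 + 0.20 × 0.25 = 0.85. On 40 sites with one TM-EMG reading each, that is 34 matches instead of 32.
- *a* from 0.70 to 0.90 and *c* from 0.10 to 0.50: the rise runs from 0.10 × 0.10 = 1 point to 0.30 × 0.50 = 15 points.

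This range restates its assumptions. It covers only the pairing route and only the normal/abnormal label. It does not cover knowledge of cohort, the neurogenic/myopathic classes or the manual measurements.

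**4. How much one label weighs.** For NEMG, one changed label is 1/20 = 5.0 points in OSA and 1/32 = 3.1 points in the healthy cohort. For TM-EMG it is 1/50 = 2.0 and 1/80 = 1.25 points. These figures show that the denominators are small; they do not measure bias.

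**5. Can it be undone?** EMG Testing Procedure has the waveforms of both methods recorded on the EMG system, and the confidentiality section keeps all data for two years after the trial. A coded re-read of stored traces is therefore possible in principle.

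**The case against.** The strongest reply is that this is a 23-participant pilot with descriptive statistics, no planned test and no decision threshold, that silence on masking is not evidence of unmasked reading, and that study records are de-identified. Much of this stands. It limits the consequence, and the reader may well be masked in practice. It does not close the gap, because descriptive agreement is as exposed to reader expectation as a test would be, and the de-identification text is not said to hide cohort or pairing.

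Using one reader for both methods is not itself a fault; it keeps differences between readers out of the comparison.

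A reader might infer three stronger points that the documents do not support:

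- *That the reader is unmasked, or is an investigator who tested the participants.* The name is removed, so the reader's role is unknown. The clause giving investigators access to trial data matters only if the reader has that access, and it carries the de-identification qualifier. It is weak support.
- *That a bias towards the expected result is established.* It is plausible, and it depends on the reader knowing the cohort or seeing the paired tracing. Nothing in the documents measures it.
- *That the damage could never be undone.* The stored waveforms allow a masked re-read, which could estimate the effect and replace the labels.

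**Conclusion.** The omission is real and bears on both endpoints. The plan permits subjective, unmasked reading to supply the TM-EMG/NEMG agreement and the comparisons of the healthy cohort with the OSA and neurologic cohorts, and inflation of both is plausible. No size can be given; the 1 to 15 point range is an illustration on assumed inputs and should not be cited as an estimate. Without a masked re-read, later analysis could not correct the first set of labels.

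The conclusion rests on two readings of the text: that one person reads both methods, as the single removed name suggests, and that no masking is required beyond what is written. It does not depend on who that person is. The change is worth making because it is cheap and because the results feed the design of the larger study; the small descriptive pilot keeps the consequence moderate.

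**What to change.** Amend Study Endpoints, Primary Endpoint, to state that:

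1. The existing research assistants export the waveforms under random codes, without initials, study identifier or cohort. Only the muscle label is kept, if it is needed for interpretation. The research assistants hold the key.
2. The same reader scores the TM-EMG files and the NEMG files in separate sessions, in random order across participants.
3. Labels and measurements are locked before the cohort and pairing codes are released.
4. Masking is reported as partial if the reader also acquired the tracings or can recognise the modality.

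The cost is a coding list for about 322 planned recordings and a slightly longer turnaround. Reading time will exceed the 54 minutes of trace, because the assessment is manual, but that reading is already planned. No extra visit, procedure or reader is needed. The amendment needs sponsor agreement and IRB approval. Masking may remain incomplete, since the two signals may look different. If reading has already been done unmasked, the same steps can be applied as a re-read of the stored waveforms.

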Description of Sites/Facilities Enrolling Participants:	All study recruitment and screening will occur at the SENTA Clinic in San Diego, CA, USA; a tertiary referral center which focuses on diseases of the head, neck, brain and spine. All EMG testing procedures will be performed in this clinic under the supervision of an expert otolaryngologist who will obtain the EMG tracings. In-Laboratory polysomnogram (PSG) studies, if required, will be performed at AmeriSleep Diagnostics in San Diego, CA, USA; a comprehensive and ACHC accredited sleep diagnostic facility.
Description of Study Intervention:	Medical device for use as novel diagnostic modality.
	Examination of the electromyographic signal from oropharyngeal muscles obtained using an investigational TM-EMG sensor attached to a rigid probe and a very fine concentric needle electrode (Ambu Neuroline 25 mm x 30G).
Study Duration:	Six months
Participant Duration:	 60 minutes for in-office screening exam. 60 minutes for in-office EMG exam. Healthy participants: One overnight stay for In-Laboratory Polysomnogram (PSG).

STUDY BACKGROUND AND RATIONALE

Electromyography (EMG) is the electrophysiological examination of muscle used for the diagnosis of suspected neuromuscular (NM) disorders such as myopathies, neuropathies, neuronopathies and neuromuscular junction disorders. ¹ Routine needle electromyography studies (NEMG) are mainly restricted to skeletal limb muscles, which are easily accessible, and are not performed routinely on less accessible muscles, such as striated muscles of the oropharynx. This limits the evaluation of neuromuscular involvement in disorders involving muscles of the oropharynx such as obstructive sleep apnea (OSA) and neurogenic oropharyngeal dysphagia. Surface EMG (SEMG) is a non-invasive EMG method that assesses muscle function by recording muscle activity from one or more electrodes placed on the surface of the skin above the muscle or muscles to be examined but lacks the signal quality to provide diagnostic information on individual motor unit morphology and recruitment. ^{2,3}

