Due to the drawbacks and limitations of both NEMG and SEMG, routine clinical EMG examination of these types of muscles is not feasible or practical. Therefore, there is a need to provide an EMG sensor that can overcome the drawbacks of NEMG and the deficiencies of SEMG to provide accurate diagnostic data for the clinical evaluation of participants with neuromuscular disorders affecting muscles located in body cavities or associated with internal organ systems.

For that reason, we propose a pilot study to examine the diagnostic utility of a novel transmembrane surface sensor, and compare signals obtained with the TM-EMG sensor to conventional NEMG signals participants from healthy volunteers to those with documented neurologic pharyngeal muscle dysfunction (ALS and muscular dystrophy) and to those with severe OSA.

STUDY SETTING

Study recruitment will occur at the SENTA Clinic in San Diego, CA, USA; a tertiary referral center which focuses on diseases of the head, neck, brain and spine. All EMG testing procedures will be performed in this clinic under the supervision of an expert otolaryngologist who will obtain the EMG tracings. In-Laboratory polysomnogram (PSG) studies will be performed at AmeriSleep Diagnostics in San Diego, CA, USA; a comprehensive and ACHC accredited sleep diagnostic facility.

STUDY DESIGN

This is a prospective, cohort, pilot study of adults from healthy volunteers to those with documented neurologic pharyngeal muscle dysfunction (ALS and muscular dystrophy) and to those with severe OSA; assessing diagnostic properties of EMG studies using a conventional needle and TM-EMG sensor in pharyngeal muscles.

OBJECTIVES and HYPOTHESIS

Primary Objective

To validate the TM-EMG sensor as a non-invasive technique for the assessment of neuromuscular function in the upper airway.

Secondary Objective

To elicit, using the TM-EMG sensor, neuromuscular findings that correlate to OSA in affected participants.

Study Hypothesis

The primary hypothesis is that transmembrane EMG (TM-EMG) examination of muscles located within internal body cavities and organ systems such as the oropharynx using the TM-EMG sensor will have similar diagnostic findings to the conventional NEMG examinations and that neurogenic changes will be observed in OSA.

Eligibility Criteria

Inclusion Criteria

- Gender: Male and or female
- Age: 18-70 years

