The principal investigator will then take his turn at assessing the same muscles. The palatoglossus will be examined in the same location using the same TM-EMG probe. Once an optimal EMG recording is obtained, the TM-EMG probe will be released off the mucosal surface and a very fine concentric needle electrode (Ambu Neuroline 25 mm x 30G) will be placed into the palatoglossus using the procedure as described below. Needle insertion will be done in a straight line through the mucosal membrane into the midpoint of the muscle at the desired depth. 1-3 needle insertions will be used to obtain a diagnostic-quality EMG tracing from each muscle. The needle is placed in the same location tested by the TM-EMG probe. Once both tracings are recorded, the contralateral palatoglossus will be tested via both TM-EMG and NEMG. The principal investigator will then obtain bilateral genioglossus EMG using the same protocol that was used for the palatoglossus.

The principal investigator will also obtain EMG data from both left and right palatopharyngeus using the TM-EMG probe and associated protocol. However, due to anticipated difficulty with gag reflex associated with the palatopharyngeus, NEMG will not be used at this site, and testing of this muscle will only be performed by the principal investigator. In total, 6 muscles locations will be tested via TM-EMG, and 4 muscle locations by NEMG.

The free-run EMG tracing for both TM-EMG and NEMG will be displayed on an oscilloscope and heard through an audio-amplifier. All EMG recordings will be made using standard gain and sweep speed settings. Waveforms for both TM-EMG and NEMG tests will be recorded on a Cadwell Sierra Summit EMG system.

We anticipate the recording time per muscle will be approximately 10 seconds. If participant exhibits intolerance during an individual muscle test, that particular muscle test will be discontinued.

The participant will be examined at the conclusion of the EMG procedures for excessive bleeding or swelling. The participant will have blood pressure, heart rate, and respiratory rate checked for stability immediately upon completion of testing and prior to discharge. The participant will be given written instructions on how to contact the research staff should any adverse events arise, such as a sore throat, fever, testing site irritation or any other study

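### MUP duration, amplitude and phases are to be analysed with both devices at four shared sites, but no paired TM-EMG versus needle comparison is planned and no labelling limits are stated for either device

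*Combined protocol and SAP*

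**What the plan says.** The Study Summary frames the question as whether the motor unit potentials seen on needle EMG can also be obtained with the TM-EMG sensor. The last paragraph of Study Background and Rationale proposes to "examine the diagnostic utility of a novel transmembrane surface sensor" and to compare its signals with needle signals.

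Under EMG Testing Procedure, the principal investigator records TM-EMG and then NEMG at the same location in the palatoglossus and genioglossus on both sides, which gives four paired sites per participant. The palatopharyngeus is tested by TM-EMG only. On settings, "All EMG recordings will be made using standard gain and sweep speed settings".

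Under Study Endpoints, Primary Endpoint, the offline reading covers spontaneous activity, "MUP morphology (number phases, duration and amplitude) and recruitment pattern". It adds that "MUP morphology will be analyzed manually". Then "Each recording will be labeled as a normal or abnormal study", and "Abnormal studies will be classified into active or chronic neurogenic changes or myopathic changes".

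The Secondary Endpoint section names two comparisons: healthy against neurologic disorders, and healthy against OSA. Under Statistical Methods, "Summary statistics will be calculated, including means or medians", with ranges, standard deviations and interquartile ranges. EMG findings in OSA are to be described. No section gives a numerical limit or reference source for either device, or a paired comparison of the two devices' measurements.

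**The concern.** The question is about two devices, but the only comparisons named are between cohorts. The label depends partly on duration and amplitude, which a different sensor position or geometry could shift. If TM-EMG values run systematically high or low, a recording can cross whatever limit the reader applies without any difference in the muscle.

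The error can go either way. The background section cites longer MUP duration as evidence of motor nerve fibre loss in OSA. An upward offset in duration could make healthy muscle look neurogenic, and a downward one could hide the finding that the secondary endpoint looks for.

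If the labels from the two devices disagree, labels alone cannot tell a stable offset, which a later study could allow for, from a sensor that does not follow the needle signal. The pilot is meant to inform a larger study, and that design would need the mean paired difference and its spread.

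**Working it through.** The plan states no offset, MUP value, SD, alpha or power, so there is no figure to reproduce. The steps below show what an offset could do and what the planned numbers could reveal.

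**Inputs from the documents.** Participants: 10 neuromuscular + 5 OSA + 8 healthy = 23 (Study Summary). Paired sites: 4 per participant (EMG Testing Procedure), so 8 × 4 = 32 in the healthy cohort and 23 × 4 = 92 overall.

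**Assumptions.** One normally distributed feature; normal limits at ±1.96 SD of healthy values; a fixed TM-EMG offset in units of that SD.

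**Step 1: false abnormals.** With net shift d, P(outside limits) = 1 − Φ(1.96 − d) + Φ(−1.96 − d). By symmetry the direction of d does not matter for a healthy recording.

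| Offset (SD) | Healthy recordings outside limits | Expected among 8 healthy, one recording each |
|---|---|---|
| 0 | 5.0% | 0.4 |
| 0.5 | 7.9% | 0.6 |
| 1 | 17.0% | 1.4 |
| 2 | 51.6% | 4.1 |

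**Step 2: hidden disease.** Take a patient group whose true mean is +3 SD (assumed). The net shift is 3 plus the offset.

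| Offset (SD) | Net shift | Detected |
|---|---|---|
| 0 | 3 | 85.1% |
| +1 | 4 | 97.9% |
| −1 | 2 | 51.6% |
| −2 | 1 | 17.0% |

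**Step 3: precision of a paired analysis.** Take one averaged TM-EMG minus NEMG difference per participant. In SDs of those differences, the 95% half-width is t(0.975, n−1)/√n for the mean and approximately t(0.975, n−1) × √(3/n) for each limit of agreement.

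| Group | n | t | Mean | Each limit |
|---|---|---|---|---|
| All | 23 | 2.074 | ±0.43 | ±0.75 |
| Neuromuscular | 10 | 2.262 | ±0.72 | ±1.24 |
| Healthy | 8 | 2.365 | ±0.84 | ±1.45 |
| OSA | 5 | 2.776 | ±1.24 | ±2.15 |

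Steps 1 and 2 are in SDs of healthy values and step 3 is in SDs of paired differences. The documents give neither, so the ratio is unknown and the two scales cannot be matched in advance. The paired analysis would itself supply the SD of the differences.

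**The case against.** The strongest reply is that this is a descriptive pilot whose endpoint is consistency of diagnosis, and that much of the evidence would surface anyway. If the planned means are reported by device, which the plan does not specify, then at complete shared sites the difference in means equals the mean paired difference. A 2 SD offset would also show as about 4 of 8 healthy participants outside the limits on TM-EMG. This stands for a large offset. It does not stand for a moderate one: at 1 SD about 1.4 of 8 are expected, against 0.4 by chance. Separate summaries also do not give the SD of the paired differences or limits of agreement.

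The label is a manual judgement on several features, including spontaneous activity and recruitment, so a hard cut-off on one feature is a simplification. That stands, and the percentages are illustrations only.

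Three stronger readings are tempting, and the documents do not support them.

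- A reader might infer that needle limits will be applied to TM-EMG. The plan names no limits for either device.
- A reader might take the background statement that surface EMG "lacks the signal quality to provide diagnostic information on individual motor unit morphology and recruitment" as an admission about this sensor. It describes conventional electrodes on skin. The protocol presents TM-EMG as a way past those deficiencies, and poor signal quality is not the same as a fixed shift.
- A reader might conclude that an offset would be read as disease. It moves only some recordings, and it can equally hide disease. A fixed offset common to all cohorts would not by itself create a healthy-versus-disease difference in the raw measurements. The threat is to the labels and to agreement between devices.

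**Conclusion.** The concern holds as a gap in the analysis, not as a demonstrated bias. The plan collects the paired measurements that its main question needs but names no analysis of them, and it leaves the labelling limits unstated for both devices. A systematic TM-EMG offset could cause false abnormal or false normal labels, and label disagreement alone could not be explained.

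Under the assumed single-feature model, false abnormals rise from 5% to between 8% and 52% for offsets of 0.5 to 2 SD. Detection of a +3 SD abnormality falls from 85% to 52% with a −1 SD offset. Whether any offset exists, and its size and direction, cannot be known from the documents.

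The change is worth making because it is cheap and uses values already planned. The 8 healthy participants could reveal a large offset but are too few to set precise limits for the device.

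**What to change.** In Statistical Methods, add a paired analysis at the four shared sites, using the principal investigator's TM-EMG and NEMG recordings:

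- Calculate TM-EMG minus NEMG for MUP duration, log amplitude and number of phases, averaged within participant.
- Report the mean difference with 95% CI and the limits of agreement for all 23 participants and for the 8 healthy participants. Show the other cohorts descriptively.
- State, before any recording is read, which limits and which source are used to label each device's recordings.
- Interpret label agreement alongside the estimated offset.

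Relabelling TM-EMG recordings after subtracting an estimated offset should be left out, or kept as exploratory only. It needs stated limits, cannot be applied cleanly to an overall manual reading, and would rest on at most 8 healthy participants.

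The cost is a little more analysis, with no new participants, visits or procedures. Estimates in the small cohorts will be imprecise. The two recordings are taken one after the other, so the limits of agreement will also contain motor-unit sampling and needle-placement variation, and the report should say so.

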Transmembrane Electromyography (TM-EMG) for the Assessment of Neuromuscular Function in the Oropharynx

Principal Investigator: [name].

Co-Principal Investigator: [name].

Subinvestigator: [name].

Sponsor: Powell Mansfield, Inc. Funded by: Powell Mansfield, Inc.

Version 2

April 4, 2019

STUDY SUMMARY

Study Description:	Transmembrane electromyography (TM-EMG) may be a feasible and
	valid non-invasive EMG technique for detecting neuromuscular (NM)
	impairment. This study will assess whether, in healthy volunteers and
	participants with known obstructive sleep apnea (OSA) and other NM
	diseases involving the oropharynx, the same characteristic motor unit
	potentials obtained on conventional needle EMG (NEMG) can be
	obtained using a TM-EMG sensor. The purpose of this study is to
	demonstrate whether the TM-EMG sensor can provide the
	same diagnostic accuracy as the concentric needle electrode for the
	diagnosis of NM diseases. Having demonstrated diagnostic similarity of
	TM-EMG to NEMG, the secondary aim of this study is to confirm that
	NM disturbance of oropharyngeal striated muscles in participants with
	OSA can be elicited with the TM-EMG sensor.

Objectives: Primary Objective: To validate the TM-EMG sensor as a non-invasive technique for the assessment of neuromuscular function in the oropharynx.

Secondary Objective: To elicit, using the TM-EMG sensor, neuromuscular findings that correlate to OSA in affected participants.

Endpoints: Primary Endpoint: Proof of diagnostic consistency using both the TM-EMG sensor and NEMG in neuromuscular disorders affecting oropharyngeal muscles.

Secondary Endpoint: Proof that participants with known OSA exhibit EMG findings different from healthy participants and that these findings can be detected using both the NEMG and the TM-EMG sensor.

- **Study Population: I**5 total participants with disorders affecting the function of oropharyngeal muscles
 - 10 participants with one of the following neuromuscular disorders:

	 ALS with the presence of bulbar symptoms
	 muscular dystrophy with the presence of bulbar symptoms
	• 5 participants with severe OSA
	8 healthy volunteer participants
Phase:	Pilot

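### The primary endpoint is agreement between TM-EMG and needle EMG, but the plan names no statistic that pairs the two methods

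*Combined protocol and SAP*

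**What the plan says.** **The question is paired.** Study Endpoints gives the primary endpoint as "Proof of diagnostic consistency using both the TM-EMG sensor and NEMG in neuromuscular disorders of the oropharyngeal muscles". The Study Hypothesis is that TM-EMG "will have similar diagnostic findings to the conventional NEMG examinations". The Study Description aims at the "same diagnostic accuracy as the concentric needle electrode", and the background states an intent to "compare signals obtained with the TM-EMG sensor to conventional NEMG signals".

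**The data are paired at acquisition.** Under EMG Testing Procedure, the principal investigator records TM-EMG and then NEMG at the same location, on left and right palatoglossus and genioglossus: four shared sites per participant. The co-investigator has already recorded TM-EMG at those four sites. The palatopharyngeus gets TM-EMG only. Each muscle may take 1-3 needle insertions, and a muscle test is stopped if it is not tolerated.

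**The outcome is mainly categorical.** "Each recording will be labeled as a normal or abnormal study". "Abnormal studies will be classified into active or chronic neurogenic changes or myopathic changes". Motor unit potential (MUP) duration, amplitude and number of phases are also read.

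**The analysis is not paired.** Statistical Methods lists the summaries: "Summary statistics will be calculated, including means or medians, minimums and maximums, standard deviations, and interquartile ranges". It adds descriptive statistics for the sleep apnea (OSA) findings. On missing data it says: "All data will be examined to determine if there are any missing or non-plausible values, and these will be removed". The comparisons named under Study Endpoints are healthy against neurologic disorders and healthy against OSA.

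**The concern.** Two methods can produce identical summaries and still disagree at the same sites. If the named analyses were carried out exactly as listed, the report could describe each method fully and leave the primary question unanswered.

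Several choices would then be made after the labels are known: which agreement measure, site or participant as the unit, whose TM-EMG recording is set against the needle, and what happens to the surviving half of a pair when the other half is missing. Each can move the result. The later multi-site study is to be designed from this pilot, so it needs an agreement estimate with honest precision.

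**Working it through.** The plan states no agreement figure, margin or power calculation, so there is nothing to reproduce. The checks below use its counts. The numbers of abnormal sites, the agreement levels and the intraclass correlations (ICC) are assumptions.

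**Inputs.** Study Summary: 10 neuromuscular, 5 OSA and 8 healthy participants. EMG Testing Procedure: 4 sites with both methods. Planned pairs: 10 × 4 = 40 neuromuscular, 8 × 4 = 32 healthy, 23 × 4 = 92 in all. Each participant has up to 4 + 6 = 10 TM-EMG recordings and 4 site-level NEMG results.

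**1. Do separate summaries fix agreement?** Let each method call A of n sites abnormal, with x sites abnormal on both. Then x runs from max(0, 2A − n) to A, and the number agreeing is n − 2A + 2x. With n = 40:

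| A | x | Sites agreeing | Agreement |
|---|---|---|---|
| 20 | 0 to 20 | 0 to 40 | 0% to 100% |
| 28 | 16 to 28 | 16 to 40 | 40% to 100% |
| 36 | 32 to 36 | 32 to 40 | 80% to 100% |

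With the finer classification, even 36 abnormal on each method does not help. Suppose both show 18 neurogenic, 18 myopathic and 4 normal. The 18 NEMG-neurogenic sites can all be myopathic on TM-EMG, the 18 NEMG-myopathic sites can be 14 neurogenic and 4 normal, and the 4 NEMG-normal sites can be neurogenic. TM-EMG totals are again 18, 18 and 4, with agreement 0 of 40.

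**2. Is overall agreement enough?** Suppose NEMG is abnormal at 36 of 40 sites and the sensor calls everything abnormal. Overall agreement is 36/40 = 90%, but it is 36/36 on NEMG-abnormal sites and 0/4 on NEMG-normal sites. In the healthy cohort it is 0/32 if NEMG is normal throughout.

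**3. What does clustering do to precision?** Effective n = 40 / (1 + 3 × ICC), with exact (Clopper-Pearson type) 95% limits on that n. At perfect agreement the lower limit is 0.025^(1/effective n).

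| ICC | Effective n | Lower limit, 100% agreement | Interval, 90% agreement |
|---|---|---|---|
| 0 | 40 | 91.2% | 76.3% to 97.2% |
| 0.25 | 40/1.75 = 22.9 | 85.1% | 70.2% to 98.5% |
| 0.5 | 40/2.5 = 16 | 79.4% | 64.8% to 99.2% |
| 1 | 40/4 = 10 | 69.2% | 55.5% to 99.7% |

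**4. Coverage.** In a beta-binomial simulation (20,000 runs, 10 × 4, true agreement 90%, ICC 0.5), the nominal 95% interval for independent pairs covered the truth 80% of the time. The effective-n interval covered 98%, but only with the true ICC plugged in. At 80% agreement with 0.25 assumed, coverage was 92% if the true ICC was 0.5 and 85% if it was 0.8.

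**The case against.** The strongest reply is that this is a declared pilot. It has no formal sample size, leaves adequate power to a later study, and introduces its list of statistics as non-exhaustive. The paired data will exist anyway, so a cross-table can be added later. Much of this stands: the plan need not be powered, and nothing in it forbids a paired analysis. It does not excuse leaving the primary estimate undefined, least of all when the endpoint is worded as proof.

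Some stronger readings are not supported:

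- *The recordings are unmatched.* They are matched by operator and location, and the labelling unit is the recording. Only the analysis role of the co-investigator's recordings and the unit of analysis are open.
- *The named statistics are of the wrong kind altogether.* Means, standard deviations and interquartile ranges suit MUP duration, amplitude and phase count. They are still one-method summaries and do not handle the labels.
- *The plan overstates its precision.* It proposes no interval and nowhere treats 40 pairs as independent. That is a risk left open, not an error made.
- *The cost of clustering is the gap between 10/10 participants (lower limit 69%) and 40/40 sites (91%).* The first concerns agreement at all four sites, the second agreement per site. They coincide only at ICC 1, so the site-level column above is the fair comparison.

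The effective-n interval is also only one option, and its coverage depends on the assumed ICC. What is needed is that clustering be handled by a method named in advance.

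**Conclusion.** The concern holds, and it should be settled before the recordings are analysed. The primary question is paired, the named statistics are not, and the named comparisons are between cohorts. Followed as written, the plan cannot support a statement about diagnostic consistency. Identical summaries are compatible with agreement from 0% to 100% in the illustration with 20 of 40 sites abnormal on each method; the range narrows to 80% to 100% at 36 of 40, but opens fully again for the finer classification.

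The loss of precision from clustering depends on an ICC that the documents do not give. Over the full range from 0 to 1, the lower limit at perfect site-level agreement falls from 91% to 69%. The 40 pairs assume that no site is lost.

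**What to change.** In Statistical Methods:

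1. Make the primary analysis a paired cross-table of TM-EMG label by NEMG label, first normal/abnormal, then the full classification. Use the principal investigator's recordings at the four shared sites and complete pairs only, with one NEMG label per site however many insertions were used. Report pairs planned, obtained and lost, by method.
2. Report percent agreement in the neuromuscular cohort, split by NEMG-abnormal and NEMG-normal sites. Show the healthy and OSA cohorts in the same format. Taking the neuromuscular cohort as primary follows the endpoint wording, but should be stated as a choice.
3. Give site-level agreement a 95% interval that allows for clustering by participant, by one method named in advance. An exact interval on effective n with a prespecified ICC, with ICC 1 as the conservative limit, is one option. Do not treat the 40 pairs as independent.
4. Summarise paired within-site differences for MUP duration, amplitude and number of phases.
5. Report the co-investigator and palatopharyngeus recordings separately.

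In the Study Summary and Study Endpoints, word the primary endpoint as an estimate of consistency rather than proof.

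The cost is a little more analysis, the loss from the primary table of sites recorded by only one method, and a less favourable statement of precision. No procedures or participants are added.
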